4.2 Study Duration

Recruitment/enrollment is anticipated to begin in August 2021 and will continue for 18 months. We estimate that up to 86 participants will have completed the study by February 2023. Visits 1-3 will be completed within a 2-3 week time period. Each participant will be considered “active” until they have completed all three laboratory visits.

4.3 Laboratory Visit 1

Participants will arrive at the BBL at approximately 1:00PM. Eligible participants will document their tobacco use that day (number, time, type) and complete lifetime and past 30 day measures of cigarillo use (flavored, non-flavored, preference), tobacco use history (e.g., cigarette smoking and menthol status), as well as baseline measures of marijuana use, depression, sensation-seeking, cigarillo risk beliefs, exposure to cigarillo flavor marketing, and demographics. Participants will provide a carbon monoxide (CO) sample and a urine sample to conduct urine cotinine analysis.

Subjective rewarding value of cigarillo flavoring. Participants will be exposed to three cigarillos. Participants who are eligible and elect to participate in the study will be required to use the study-provided cigarillos during this portion of the visit in our smoking lab. One cigarillo will be non-flavored, meaning no characterizing flavors were added to the tobacco. Two will contain sweet flavoring (fruit and cream). All three will have the same characteristics, only differing by flavor. Participants will take 2 puffs from the non-flavored cigarillo, the fruit-flavored cigarillo, and the cream-flavored cigarillo. The exposure to the three cigarillos will be separated by 20 minutes each, and the order of the three exposures will be counterbalanced. Order will be stratified by sex and smoking status. After each of the three cigarillo exposures, participants will complete measures of subjective reward. Visit 1 will occur in the afternoon versus the morning to increase the likelihood that participants who smoke cigarettes smoke normally throughout the day and can rate flavoring/no flavoring in the absence of significant withdrawal symptoms. After Visit 1, participants will be scheduled for Visit 2. Participants who use tobacco (e.g., combustible cigarettes, e-cigarettes, cigars, blunts) or combustible marijuana will be given instructions to abstain from tobacco products and combustible marijuana 10 hours prior to BBL Visit 2.

CONFIDENTIAL

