7.4.3 Outcome variables

Subjective rewarding value of cigarillo flavoring will be measured with the Cigarette Evaluation Scale (CES) adapted for cigarillo use. The CES is an 11 item Likert-format (1=not at all to 7=extremely) self-report instrument with established validity and reliability ($\alpha > .80$). We will focus on the satisfaction subscale. Primary Outcome measured at visit 1.

Relative reinforcing value of cigarillo flavoring will be measured with a validated choice paradigm, evaluating the preference for sweet flavored vs non-flavored cigarillos. RRVF will be defined by the breakpoint (highest trial completed across 10 trials to earn puffs for sweet flavored versus non-flavored cigarillos) Primary Outcome measured at visit 2.

Absolute reinforcing value of cigarillo flavoring is operationalized as the number of sweet flavored versus non- flavored cigarillo puffs consumed during the ad libitum smoking session. A research assistant will videotape, monitor, and count the number of cigarillo puffs taken during the 90- minute period. The primary comparison is the amount of consumption (puffs) of the sweet flavored versus non-flavored cigarillo. Primary Outcome measured at visit 3.

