Aim 1 H2 will determine whether the relative reinforcing value of a sweet flavored cigarillo is greater than that of a non-flavored cigarillo among young adults. H2 will test whether participants “work harder” for sweet flavored cigarillo puffs than non-flavored cigarillo puffs (i.e., higher relative reinforcing value) as measured by a choice task. Participants will be given the choice to “work for” sweet flavored puffs at an increasing behavioral cost (more mouse clicks) or non-flavored puffs at a low fixed cost. The outcome variable used for this analysis is a breakpoint representing the highest level of work a participant will perform for a puff of a sweet flavored cigarillo. Flavor is inherent in the breakpoint outcome and will be assessed using a GLM.

Aim 1 H3 will determine whether the absolute reinforcing value of a sweet flavored cigarillo is greater than that of a non-flavored cigarillo among young adults. H3 will test whether participants take more puffs from a sweet flavored cigarillo versus a non-flavored cigarillo during the ad-libitum smoking session. The outcome measure is puff counts of sweet flavored and non- flavored cigarillos, and preference will be estimated as a rate-ratio using negative binomial mixed models.

CONFIDENTIAL

This material is the property of the University of Pennsylvania. Do not disclose or use except as authorized in writing by the study sponsor

Sample Size / Power. The proposed study is a within-subjects design. The sample size is driven by the test for H3. Because we have three experimental outcomes, we will Bonferroni correct our global alpha of 5% for three tests. Informed by the effect size of our prior study investigating e-cigarette flavoring (Cohen's d of 0.5) with a small within-subjects correlation (negative binomial model) of $r=0.13$. A sample of 86 yields 80% power to detect an effect size of 0.5, testing at alpha = 0.017.

8 Risks / Benefits

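### Fixed Bonferroni over the three primary tests is valid, but Holm's step-down would hold the same 5% family-wise error at N = 86 and lift H3 power by anything from almost nothing to about 10 points

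*Combined protocol and SAP*

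**What the plan says.** Section 7.4.3 (Outcome variables) labels all three outcomes primary: the satisfaction rating ("Primary Outcome measured at visit 1"), the choice-task breakpoint ("Primary Outcome measured at visit 2") and the ad-libitum puff count at visit 3.

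Section 7.5 (Analytic Plan) sets the multiplicity rule: "Because we have three experimental outcomes, we will Bonferroni correct our global alpha of 5% for three tests". On sample size it says: "The sample size is driven by the test for H3", and "A sample of 86 yields 80% power to detect an effect size of 0.5, testing at alpha = 0.017". The effect size is a Cohen's d of 0.5 from the team's earlier e-cigarette study, "with a small within-subjects correlation (negative binomial model) of" 0.13.

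The plan gives no step-down or gatekeeping rule, no power for H1 or H2, no correlation between the three outcomes, and no statement of one- or two-sided testing.

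Two of the tests are loosely defined:
- **H1.** Section 4.3 collects ratings for two sweet cigarillos (fruit and cream) and one non-flavored. Section 7.5 does not say which sweet rating, or which combination of the two, enters the test.
- **H2.** Section 7.5 says only: "Flavor is inherent in the breakpoint outcome and will be assessed using a GLM". It gives no null value for the breakpoint.

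**The concern.** With fixed Bonferroni, H3 is judged at 0.05/3 even when H1 and H2 are clearly positive. Section 2.1 expects all three effects to be positive, and in that setting a fixed split leaves power unused. Holm compares the smallest p-value with 0.05/3, the next with 0.05/2 and the last with 0.05, stopping at the first failure. H3 could then be tested at up to 0.05 with the family-wise limit unchanged.

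What is at stake is part of the 20% chance of missing a true H3 effect, on the outcome that sizes the trial. Under Holm, however, H3's threshold depends on the H1 and H2 p-values. An ill-defined H1 or H2 test, which under Bonferroni harms only itself, could then also weaken the protection on H3.

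**Working it through.** **Inputs from section 7.5:** family-wise alpha 0.05, three tests, N = 86, d = 0.5, r = 0.13, H3 power 80% at 0.017. **Assumed, because not stated:** two-sided tests, H1 and H2 power, and the correlation between test statistics.

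**1. The plan's own 80%.** A paired formula uses dz = d / √(2(1 − r)) = 0.5 / √1.74 = 0.379.
- 86 analysed, r = 0.13, alpha 0.05/3, noncentral t: 85.6%.
- 86 analysed, r = 0: 79.7%.
- Required n with r = 0.13, normal formula: ((2.394 + 0.842) / 0.379)² ≈ 72.9, so 73; and 73 / 0.85 = 85.9, so 86. This also gives 80%, but it makes 86 the number recruited, whereas section 5.2 makes 86 the number with complete data.

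The 80% is therefore reproducible, but not with 86 completers and r = 0.13 in this formula. The negative binomial calculation cannot be rebuilt, because no mean or dispersion is given. Both baselines are carried forward.

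**2. Ceilings under Holm from 80%.** H3's noncentrality is 2.394 + 0.842 = 3.236.
- One other hypothesis certain to be rejected, so H3 is tested at 0.025: Φ(3.236 − 2.241) = 84.0%.
- Both certain to be rejected, so H3 is tested at 0.05: Φ(3.236 − 1.960) = 89.9%.

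**3. H3 power under Holm when the others are not certain.** Simulation of 1,000,000 equicorrelated normal triples per scenario, with the other tests' power defined at 0.05/3:

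| Other two tests | corr. 0 | 0.3 | 0.5 | 0.9 |
|---|---|---|---|---|
| Both real, 99% power | 89.9 | 89.7 | 89.8 | 89.9 |
| Both real, 80% | 88.0 | 87.0 | 86.5 | 84.5 |
| Both real, 50% | 84.8 | 83.6 | 82.7 | 80.2 |
| One absent, other 99% | 84.1 | 84.1 | 84.1 | 84.1 |
| One absent, other 80% | 83.3 | 83.0 | 82.8 | 82.1 |
| One absent, other 50% | 82.1 | 81.6 | 81.2 | 80.1 |
| Both absent | 80.2 | 80.1 | 80.1 | 80.1 |

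**4. From the 85.6% baseline, correlations 0 to 0.5.** One other effect real at 80-99% power: 87.6-88.9%, a gain of 2-3 points. Both real at 80-99%: 90.2-93.2%, a gain of 5-8 points.

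**5. Error rates.** Holm's family-wise error did not exceed 5.0% in any scenario. With the other two effects real, the error on a single true null rises from 1.7% under Bonferroni to about 3.4-4.2% when each has 80% power, and to at most 5% when both are almost certain to be rejected.

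**6. Dependence of H3 on H1.** Suppose H1 used the higher of the two sweet ratings, which the plan does not say. With no true flavor effect, 86 normal rating triples and correlations of 0.13 to 0.8 between ratings, a paired t-test at 0.05/3 rejects about 94% of the time. Under Holm, if H1 is falsely rejected and H2 is null, H3's own error is about 2.6% instead of 1.7%. If H1 and H2 are both rejected for reasons of definition, it reaches 5%.

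**The case against.** The strongest reply is that this is a preference. The plan prespecifies a valid correction and sizes the trial on it. Fixed Bonferroni also has real merits: each hypothesis stands alone, and 98.3% intervals, including one for the H3 rate ratio, agree with the test decisions. This stands, and it is why the point is optional.

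Second, the gain may be small. All three outcomes measure sweet-flavor preference in the same people, so high correlation is plausible. At a correlation of 0.9 with both others at 50% power, H3 power is only 80.2%. This also stands. A reader might infer from the favorable scenarios that Holm would bring H3 to nearly 90%. The documents do not support that, because they state no H1 or H2 power. That H3 drives the sample size suggests the other two tests were thought at least as well powered, but does not show it.

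Third, timing. Section 4.2 says: "We estimate that up to 86 participants will have completed the study by February 2023". Data may already have been seen, and puffs are counted live by staff (section 4.5). The documents do not settle whether outcome data have been examined, so the change must be conditional.

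Fourth, Holm makes H3 depend on tests that are not fully specified. This stands and shapes the fix. A reader might go further and infer that H1 is already biased, because section 4.4 picks the highest-rated sweet flavor for later visits. Section 7.5 does not say that H1 uses that rating, so this is a risk to close and not a finding.

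**Conclusion.** The point holds as an optional improvement. Holm keeps the 5% family-wise error, loses no rejection that Bonferroni would make, and leaves N = 86 unchanged. Taking the stated 80% as given, H3 power becomes about 82-84% with one other real effect at 80-99% power and about 84-90% with both, for correlations of 0 to 0.9. It stays close to 80% if neither is real, or if the others are weak and highly correlated with H3. From an 85.6% baseline the gain is 2-3 or 5-8 points at correlations up to 0.5. These figures rest on two-sided tests and approximately normal test statistics; one-sided testing moves H3 power under Holm by at most about 1 point.

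A reader might infer that Bonferroni is wrong here, or that the trial is underpowered because of it. Neither follows. The 0.017 is 0.05/3 rounded, and the stated 80% is power under Bonferroni. Confidence is high in the method and its error control, and low in the size of the benefit to this trial.

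**What to change.** If no outcome data have been examined, replace the Bonferroni sentence in section 7.5 with: *H1, H2 and H3 will be tested by the Holm step-down procedure at a family-wise alpha of 0.05.* Document the adoption date as before any outcome data were examined. If outcome data have been examined, keep the prespecified Bonferroni rule.

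In the same change:
- define the H1 contrast so that it is not the higher of the two sweet ratings, for example the mean of the fruit and cream ratings against the non-flavored rating;
- state the null value for the H2 breakpoint test;
- state whether the tests are one- or two-sided;
- keep the sample size based on 0.05/3;
- say how any reported confidence intervals relate to the Holm decisions.

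The cost is a few sentences and a dated record. There are two statistical downsides. Simple 98.3% intervals may not mirror Holm decisions at the second and third steps. The error rate on a single true null also rises, as shown in the working, though it stays within the family-wise limit. The H1 and H2 definitions are needed under Bonferroni too; under Holm they also protect H3.

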8.1 Potential Study Risks

The potential risks to participants, their likelihood and seriousness, and strategies to mitigate risks are described below. Participants can choose, as an alternative, to not enroll in this study. Overall, there is minimal risk for serious adverse reactions as a consequence of enrolling in this study. Adverse reactions/AEs will be collected, assessed, and reported as per the study protocol (see section 8: Safety and Adverse Events), federal law, and University of Pennsylvania regulations.

Cigarillo Smoking: The study-provided cigarillos you will be asked to smoke are commercially available. During the course of this study, participants will smoke flavored and/or unflavored cigarillos. At Visit 1, participants will take 6 puffs of a cigarillo. At Visit 2, participants will take 10 puffs of a cigarillo. At Visit 3, the number of puffs participants take is up to them. Some participants may experience certain symptoms while taking puffs of cigarillos, like nausea, dizziness, and/or rapid heartbeat. These feelings are typically mild and relatively short-lived. These symptoms are more common among individuals who have not have prior exposure to tobacco products and thus have not had previous exposure to nicotine. The chances that participants will experience these symptoms are less likely because they have had prior nicotine exposure. The informed consent form states that, if participants do experience these symptoms, they may let a member of the research staff know immediately and will be permitted to extinguish their cigarillo, even if they are in the middle of a smoking task.

Withdrawal Symptoms: Participants may experience uncomfortable withdrawal symptoms during their 10-hour tobacco abstinence. In preparation for the 10-hour tobacco abstinence, participants will receive tips for remaining abstinent (e.g., coping with withdrawal and craving, smoking triggers, coping with stress). Participants will also be reminded that these symptoms will be short-lived and that they will receive incentives for participation.

Reproductive Risks: Smoking can cause serious harm to unborn children or children who are breast-feeding. Female participants are asked to use a medically accepted method of birth control (such as IUD, birth control pills, condoms, etc.) while participating in the study. Further, female participants, and those assigned as female at birth, will be asked to administer a simple, one-step hCG pregnancy test and informed that if they are (or believe they may be) pregnant that they will not be eligible to participate in the research study. If a female participant becomes pregnant over the course of the trial, they will be immediately withdrawn. It will also be recommended that the participant seek consult from an obstetrician or maternal-fetal specialist about the dangers of smoking while pregnant.

Assessments: Some participants may experience some emotional distress during the assessments due to learning their carbon monoxide levels or seeing how many cigarillos they smoke. These events happen very rarely and in almost all cases are short-lived and of low intensity. If a participant does exhibit a high level of emotional distress, however, they will be offered contact information for mental health services in the area.

CONFIDENTIAL

This material is the property of the University of Pennsylvania. Do not disclose or use except as authorized in writing by the study sponsor

Email Communications: In this research study participants may prefer to receive appointment reminders via email or submit questions related participation via email. Email is not a secure means of communication. Email messages travel across the Internet passing through multiple computers before reaching their final destination. It is not possible to know whether an email a participant sends will be viewed along the way. Additionally, if sent messages are not deleted, an email provider may have an archive of everything that is sent. If someone gets access to an email account (for example, a participant's family member), they could see archived messages. There are many other ways in which emails are not secure—these are only selected examples. To manage this risk the informed consent form will include specific language to educate research participants on the privacy risks involved in email communications. Participants will also be explicitly instructed to only use email communications for routine matters and never for personal or confidential messages or questions.

Confidentiality and Loss of Privacy: See section 9.6.1 and 9.6.2 for methods in which Confidentiality and Subject Privacy/Protected Health Information will be secured and maintained.

8.2 Potential Study Benefits

Young adults may benefit from participation by knowing that they are contributing to research that can ultimately help protect young adults like themselves from becoming regular cigarillo smokers. The proposed study is expected to yield new knowledge regarding the subjective, objective, and behavioral impact of sweet flavoring on cigarillo use among young adults, while controlling for other variables that may also impact the use of sweet flavored cigarillos. The findings will inform public health interventions and regulatory actions to reduce cigarillo use in this vulnerable population. The benefits outweigh the minimal risks associated with participation.

8.3 Risk/Benefit Assessment

The potential benefits of this study outweigh the potential risks. There is only a minimal risk of experiencing study-related AEs or SAEs by enrolling in this trial. The findings from this study will inform public health interventions and regulatory actions regarding the appeal of flavoring in cigarillos.

8.3.1 Adequacy of Protection against Risks

Informed Consent. Informed consent/HIPPA forms will be signed electronically on REDCap or at Laboratory Visit 1 before any research activities are completed. Trained staff will provide a study overview, including the risk and benefits of being in the study. Staff will respond to all questions and inform potential participants that participation is voluntary. Preliminarily eligible adult smokers will be asked to provide informed consent for participation. After receiving informed consent, participants will provide a urine sample to assess drug use and/or pregnancy, which are exclusions for participation. Participants will receive a copy of their signed consent form.

Oversight and Monitoring. The Institutional Review Board at the University of Pennsylvania will monitor the protection of human subjects and the safe and secure collection and storage of data. This committee will assess the study before initiation and then annually at the time of Continuing Review. The IRB will ensure the scientific, technical, and statistical soundness of the research and guarantee that methods for the ethical and safe treatment of human subjects are in place.

Participant Safety. Eligibility criteria for this study will exclude any individual who would be at risk of adverse effects from participation in this study. Participant safety begins with the PI's thorough training and ongoing supervision of the project staff and study procedures. Weekly meetings will ensure an understanding and adherence to the study goals and data collection and management procedures. Personnel training by the PI will be considered to be of the highest priority and will

CONFIDENTIAL

This material is the property of the University of Pennsylvania. Do not disclose or use except as authorized in writing by the study sponsor

be addressed prior to the start of the study and on an ongoing basis. Training will help ensure that all processes and procedures for data collection and management are correctly applied and utilized. Specifically, but not exclusively, this training will ensure that research personnel understand the study's goals and objectives, data collection process, confidentiality, participant safety, all case report forms (CRFs), the manual of procedures (MOP), database software and the data management system (DMS), and all applicable standard operating procedures (SOPs) to attest that the study is conducted in a proper manner. Training will span study recruitment approaches, screening, assessment, follow-up of rescheduled participants, data entry and storage, and tracking study incentives.

Data Management. The CIRNA Data Management Core will be responsible for the data management system, the operational facets of this study, quality assurance, and data storage.

Data Collection, Processing, and Management. All data collection, processing, and management procedures will be standardized in a detailed Manual of Procedures (MOP). Hard-copy surveys will serve as source documents. All data are entered into a database located upon the secure server with dedicated uninterrupted power at the CIRNA. All indicated data entry and processing operations will be performed using Data Management System (DMS) software. Study personnel will access the menu driven DMS software to perform specific operations. For example, the DMS functionality will include subject tracking, data entry, data validation, and query tracking, standard reports, and tracking of all major study milestones (e.g., assessment and visit disposition), and the counterbalanced sequence of the order of flavors on laboratory visit 1.

Quality and Data Safety Assurance Practices. The PI will conduct training to ensure that all processes and procedures for data collection and procedures for data collection, processing, and storage are correctly applied and utilized. Confidential participant information will be collected and entered into the database. When this information exists on paper (e.g., updated contact information, alternative contact information) it will always be filed under lock and key. Upon entry of this data into the database, an auto-study ID will be generated. The auto-study ID will then generate and be linked to a participant ID in a separate table. Thus, contact information will never exist in the same DMS table as a participant ID. No one can gain access to an individual database unless they have been explicitly granted a user ID and password. The Center's database server and individual study databases have never been compromised as a result of the extremely rigorous and secure network firewall technologies. The secure servers are located in a specially designed, highly secured facility with dedicated uninterrupted power supply. Access to this server facility is strictly limited.

Adverse Event Reporting. In accordance with NIH and IRB guidelines, this protocol will employ the following mechanisms for adverse event reporting: (1) alert the IRB of any and all reports of serious adverse events; (2) inform all members of the study team of any and all reports of serious adverse events; (3) notify the NIH of any actions taken by IRB with regard to data safety monitoring.

9 Safety and Adverse Events

